6.9.3 Visit 7 (Cycle 3)

- Timing:
 - Ideal: Day 85 to 89 (Cycle 3, days 1-5)
 - Allowable: up to day 105 (Cycle 3, days 1-21)
- Follow-up Procedures:
 - Review of adverse events or changes in medical history since the prior visit
 - Review of concomitant medications
 - Inquire about change in sexual partner
 - Collect and review daily diary for completeness
 - Subject completion of Treatment VAS questionnaire (Appendix E)
 - Dispense additional diaries and feminine hygiene products as needed
 - Physical examination and testing
 - High sensitivity urine pregnancy test (if positive, see Section 7.4)
 - Blood pressure, pulse and weight
 - Any clinically indicated physical examination
 - Clinically verify presence of IUS by palpation or direct visualization of strings (for missing strings management see Section 6.13 and Appendix G)
 - Chlamydia and gonorrhea testing for any subject following a change in sexual partner since the last study visit.
 - Women with positive tests should be contacted and receive treatment as soon as possible without waiting for the next study clinic visit
 - Collect all feminine hygiene products collected between Day 57 and Day 84
 - Interview subject for feminine hygiene collection compliance
 - Collect venous blood for:
 - Hemoglobin/hematocrit and ferritin
 - AH assay sample

- Instruct her to start collecting all used feminine hygiene products with evident blood between Day 141 and Day 168
 - Day 141 would include any products initiated prior to going to sleep the night before but removed on Day 141
 - Any products initiated the evening of Day 168 but removed the next morning would not be collected
- Schedule next appointment (Visit 8) ideally for Day 169 to Day 174, but up to Day 189 is allowed

6.9.4 Contact Day 133 to Day 140

- Remind subject to:
 - Start collecting all used feminine hygiene products with evident blood collection between Day 141 and Day 168
 - Day 141 would include any products initiated prior to going to sleep the night before but removed on Day 141
 - Any products initiated the evening of Day 168 but removed the next morning would not be collected
 - Dispose of any used products from prior to Day 141 or after Day 168
 - Confirm date and time for Visit 8 appointment

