6.10 Study Treatment Phase Completion/Early Discontinuation (Visit 8)

- Timing:
 - Completion of 6 cycles of LNG20 IUS use
 - Ideal: Day 169 to Day 174 (within 5 days of completing 6 cycles)
 - Allowable: up to Day 189 allowed (up to 21 days after completing 6 cycles)
 - Early discontinuation
- Procedures:
 - Review of adverse events or changes in medical history since the prior visit
 - Review of concomitant medications
 - Inquire about change in sexual partner
 - Collect and review daily diary for completeness

- Subject completion of Treatment VAS questionnaire
- High sensitivity urine pregnancy test (if positive, see Section 7.4)
- Weight, pulse and blood pressure
- Any clinically indicated physical examination
- Clinically verify presence of IUS by palpation or direct visualization of strings (for missing strings management see Section 6.13 and Appendix G)
- Chlamydia and gonorrhea testing for any subject following a change in sexual partner since the last study visit.
 - Women with positive tests should be contacted and receive treatment as soon as possible
- Breast and pelvic exam (if not performed within the last 3 months)
- IUS removal
 - If participant has contraindication to continuing IUS use or desires removal then perform IUS removal procedure
 - If no indication for removal, discuss option of continuing IUS or removal; remove IUS for all women that desire to discontinue IUS
- Retain all removed or expelled IUSs as described in the Study Reference Manual
- Collection of feminine hygiene products:
 - If completed full protocol: collect all products collected between Day 141 and Day 168
 - If early discontinuation coinciding with Visit 7 (Cycle 3): collect all products collected between Day 57 and Day 84
 - If early discontinuation not coinciding with a complete Visit 7 or Visit 8 collection window: no product collection
- If collected feminine hygiene products:
 - Interview subject for feminine hygiene collection compliance
 - Collect venous blood for:
 - hemoglobin/hematocrit and ferritin (if not obtained within the prior 6 weeks)
 - AH assay sample

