5.3.3 Missing Data for MBL

- A MBL assessment by AH may not be collected for Treatment Phase Cycle 3 and Cycle 6 in which a subject reported being amenorrheic (no spotting/bleeding) for the 28-day collection interval on the CRF for AH Menstrual Blood Loss Assessment; in this case the corresponding MBL value will be set to 0 mL. Additionally, the participant may report spotting only or light bleeding on her diaries with no feminine hygiene products used; in this case the corresponding MBL value will be set to 0 mL
- For a Treatment Phase missed Visit 7 (Cycle 3) or missed Visit 8 (Cycle 6), no imputation of MBL from diary data alone will be conducted.
- For the evaluations of MBL, the last observation carried forward (LOCF) method will be used for imputation. If MBL data in Cycle 3 are available but no MBL data in Cycle 6 are available or Cycle 6 is invalid, then MBL data in Cycle 3 will be used as End of Study MBL.
- Additional imputation method(s) might be explored for sensitivity analysis when deemed necessary

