- If, during on-study contact with the subject she reports that the IUS is no longer in place, the date of reported expulsion/removal if known, or if unknown the date of contact minus 1 day, will be used as the last date associated with IUS use.
- In the cases of subjects who are lost to follow-up or withdraw consent prior to Visit 8 and a last contact date is available, the last contact date- date of insertion ($i_{usindt}+1)/28$ will be used. If not contact date after insertion is available then date of IUS insertion + 1 day will be used as the last date associated with IUS use.

Similarly, for subjects who had a successful IUS insertion but who have not yet had any post-insertion data (e.g., Visit 6, Visit 7, Visit 8, unscheduled visit) retrieved at the site which could be used to directly calculate duration of use, the IUS insertion date +1 day will be used as the last date of IUS use for the purpose of analysis. For the summary of duration of product use, all subjects with ≥ 1 days of product use, as defined in this section, will be included in the calculations.

5.5 28-Day Cycles of Use Calculation

In addition to the calculation of 28-day cycles based on last date of IUS use as described in [Section 5.4](#), each recorded diary date between the IUS insertion date and the last calculated date of product use, inclusively, is compared to the IUS insertion date in order to calculate cycle number and day. Duration of use expressed as the number of 28-day cycles is then calculated as the maximum duration (ceiling value) between the IUS insertion date and last recorded diary date.

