9.1 Menstrual Blood Loss

This study will utilize the AH method to assess MBL. During the Screening Phase all feminine hygiene products used during a menses with any evident bleeding will be analyzed. Baseline MBL will be the average of the Screening cycles evaluated. Two of three cycles must have ≥ 80 mL MBL to qualify for enrollment (Treatment Phase); if the first two cycles qualify a third cycle will not be evaluated. During the Treatment Phase, all feminine hygiene products use only during Cycle 3 (Days 57-84) and Cycle 6 (Days 141-168) will be collected for analysis and used to determine efficacy. All values of MBL reported by the lab for the above cycles for both validated and unvalidated feminine hygiene products will be included in the analysis, unless analyzed beyond the 56 days of validated stability.

MBL assessment measured from all collected feminine hygiene products will be included in the primary analysis and only study-specific validated feminine hygiene products in the supportive analyses.

The study-specific feminine hygiene products are:

- Tampax Regular Tampons with flushable applicator
- Tampax Super or Super Plus tampons with flushable applicator
- Kotex Regular Maxi Pads;
- Kotex Super Long Maxi Pads;
- Kotex Overnight Maxi Pads with Wings.
- Carefree Body Shape Pantiliners with Actifresh, Extra Long

A MBL assessment by AH may not be collected for Treatment Phase Cycle 3 and Cycle 6 in which a subject reported being amenorrheic (no spotting or bleeding) on the CRF for AH Menstrual Blood Loss Assessment; in this case the corresponding MBL value will be set to 0 mL. In the case that no feminine hygiene products were used by the participant due to spotting only the MBL value will be set to 0 mL.

Any feminine hygiene product collection would be considered “invalid” for the following:

- Analyzed beyond the 56 days of validated stability (from start of feminine hygiene collection).
- Any feminine hygiene product collection for a Treatment Phase cycle for which it was discovered during the post-collection interval study visit (i.e., Visit 7 for Cycle 3 and Visit 8 for Cycle 6) that the study IUS was not present
- Technical issue at the lab in analyzing the product leading to unreportable results

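### SAP 9.1 voids a Cycle 3 or Cycle 6 blood-loss result when the IUS is found absent at the next visit, whenever it was lost, and no planned analysis keeps the measured value

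*SAP*

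**What the plan says.** SAP 9.1 fixes the collection intervals: "Cycle 3 (Days 57-84) and Cycle 6 (Days 141-168) will be collected for analysis and used to determine efficacy". It then lists grounds on which a collection is invalid. One is "Any feminine hygiene product collection for a Treatment Phase cycle for which it was discovered during the post-collection interval study visit", continued as "i.e., Visit 7 for Cycle 3 and Visit 8 for Cycle 6) that the study IUS was not present". The date of loss plays no part in that ground.

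The visits at which absence is discovered come later than the collection. Protocol 6.9.3 gives Visit 7 as "Allowable: up to day 105 (Cycle 3, days 1-21", and Protocol 6.10 gives Visit 8 as "up to Day 189 allowed (up to 21 days after completing 6 cycles".

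SAP 5.3.3 states the consequence. Where a Cycle 3 value is available and Cycle 6 is missing, or "Cycle 6 is invalid, then MBL data in Cycle 3 will be used as End of Study MBL". SAP 10.1 uses last observation carried forward in the MITT analysis, which is the principal one, and in both ITT analyses. SAP 6 and 9.2 carry the baseline forward in the ITT only when neither Cycle 3 nor Cycle 6 yields a result.

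Two other statements carry no exception for an absent IUS. An earlier sentence of SAP 9.1 includes every laboratory-reported value unless it was analysed beyond 56 days. SAP 9.2 takes the last recorded post-baseline value as end of treatment.

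**The concern.** The trigger is the state of the IUS on the visit day. What matters for the endpoint is whether the IUS was in place on the collection days. The two can differ in either of two ways.

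- **Loss after collection ended.** A complete collection made under treatment is discarded because of something that happened later.
- **Unrecognised loss before or during Cycle 6.** The products were collected, but the value is set aside and the earlier Cycle 3 value is scored. Protocol Appendix G notes that a rise in menstrual flow may point to expulsion, so the value set aside may be the worse of the two. The ITT analyses would normally be expected to reveal this, but they carry Cycle 3 forward in the same way.

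Because SAP 9.1 states both that only the 56-day limit excludes a reported value and that an absent IUS voids it, two programmers could score the same woman differently on the primary endpoint.

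**Working it through.** **Step 1: timing.** The last collection days are Day 84 and Day 168 (SAP 9.1). The latest visit days are Day 105 and Day 189 (Protocol 6.9.3 and 6.10). The gap is 105 − 84 = 21 and 189 − 168 = 21 days. At the end of the ideal windows it is 89 − 84 = 5 and 174 − 168 = 6 days.

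**Step 2: what the wording does to each case.**

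| Case | SAP 9.1 as worded | MITT | ITT analyses |
|---|---|---|---|
| Lost after Day 168, absent at Visit 8, Cycle 3 valid | Cycle 6 void, though made under treatment | Cycle 3 scored | Cycle 3 scored |
| Lost unrecognised before or during Cycle 6, products collected, Cycle 3 valid | Cycle 6 void | Cycle 3 scored | Cycle 3 scored |
| Cycle 6 void, no valid Cycle 3 | No valid value | Arguably leaves | Baseline carried forward: failure |
| Lost after Day 84, absent at Visit 7, discontinued with no Cycle 6 | Cycle 3 void, though made under treatment | Arguably leaves | Baseline carried forward: failure |
| As above, but a valid Cycle 6 follows a permitted reinsertion | Cycle 3 void | Cycle 6 scored; primary endpoint unaffected | Same |

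The MITT entry is only arguable because SAP 6 asks for at least one MBL assessment and does not say whether a voided one counts. A baseline value carried forward is a failure by definition, since it cannot be half of itself or less.

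**Step 3: expected number of post-collection losses.** Protocol 7.1.5 cites 3.9% expulsion in the first year. I assume a constant hazard: h = −ln(1 − 0.039)/365. The expected number over a gap of w days is N × (1 − exp(−h·w)).

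| Gap | N = 85 | N = 100 |
|---|---|---|
| 5 days | 0.05 | 0.05 |
| 6 days | 0.06 | 0.07 |
| 21 days (every visit at the limit) | 0.19 | 0.23 |

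If early expulsion were more frequent, say 8% to 12% per year (an assumption, not a document figure), the 21-day row becomes 0.41 to 0.73. Counting the 28 collection days as well (28 + 21 = 49 days, at 3.9%), it becomes 0.45 for N = 85 and 0.53 for N = 100.

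The share of losses found at Visit 8 that came after collection cannot be fixed from the documents. With uniform timing and a Day 189 visit it is 21/49 = 43% counting from Day 141. It is 21/100 = 21% counting from a Visit 7 on Day 89, the last ideal day for that scheduled IUS check. I rest nothing on it.

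**Step 4: the plan's precision and the boundary.** The normal-approximation lower bound is p − 1.96·√(p(1 − p)/n). At p = 0.80 it gives 71.5% for n = 85 (Protocol 9.1 states 71.5%) and 71.2% for n = 80 (SAP 4 states 71.2%), so both figures reproduce. Against the 70% criterion:

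| n | Successes | Lower bound | Meets 70% |
|---|---|---|---|
| 80 | 64 | 71.2% | yes |
| 80 | 63 | 69.8% | no |
| 85 | 68 | 71.5% | yes |
| 85 | 67 | 70.1% | yes |
| 85 | 66 | 68.8% | no |

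One reclassified woman moves the bound by about 1.4 points.

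**The case against.** **The wording may mean something narrower.** The ground could be read as absence during the cycle, merely discovered at the visit. That is a possible intention, but the SAP does not say it. This weakens the charge to one of unclear wording on the primary endpoint; it does not remove it.

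**A reader might infer that results are discarded once they are known.** The documents do not support that. IUS presence is checked at the visit where products are handed in and the venous sample is drawn, and the products go to the laboratory afterwards (Protocol 6.1, SAP 3). The trigger normally precedes the assay, and the rule is prespecified.

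**A reader might infer that the rule systematically turns failures into successes.** It can do so where Cycle 3 was a success and Cycle 6 was not. But without a valid Cycle 3 value the ITT records a failure, and a voided Cycle 3 changes nothing if a valid Cycle 6 follows.

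**Recognised losses are largely outside the problem.** Women are told to call if the IUS is expelled (Protocol 6.8.2). Early discontinuation that does not coincide with a complete collection window yields no products (Protocol 6.10). What remains is mainly unrecognised loss and loss after collection.

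**Dating the loss is not simple.** SAP 5.4, for a woman who reports the IUS gone, uses "the date of reported expulsion/removal if known, or if unknown the date of contact minus 1 day". For any Visit 8 on Day 170 or later that puts an unknown loss on Day 169 or later, after the window. SAP 5.3.6, which sets a wholly missing expulsion date to the last clinic visit, could do the same. This objection stands: a correction that leaned on those imputations would declare doubtful collections valid.

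**Conclusion.** The concern holds as a defect of definition with a small expected effect. As worded, SAP 9.1 can void a primary-endpoint result obtained wholly under treatment. It can also replace a measured Cycle 6 value by an earlier one in the MITT and both ITT analyses. The per-protocol and supportive MITT sets are subsets of the MITT and do not restore the value. SAP 5.3.3 only allows that further imputation methods might be explored. The rule also conflicts with the inclusion sentence in its own section.

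The direction of bias is not fixed. On a constant hazard at 3.9% per year, about 0.05 to 0.23 post-collection losses are expected per visit; unrecognised losses before or during Cycle 6 add to that. A single woman would change the conclusion only near the boundary: at n = 80 with 64 successes she would, while at n = 85 with the planned 68 she would not. I rate it minor to moderate. It deserves correction because it concerns the primary endpoint and the correction is cheap, not because it is likely to decide the trial.

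**What to change.** Amend SAP 9.1, with matching text in 5.3.3 and 10.1:

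1. A collection is invalid for IUS absence only if loss on or before its last day (Day 84 or Day 168) is documented or cannot be excluded. A documented loss after that day leaves the MBL valid.
2. For this purpose, do not use the date imputations of SAP 5.4 or 5.3.6. Treat an unknown loss date as within the window.
3. In the ITT analyses, use the measured Cycle 6 MBL where one exists, and do not substitute Cycle 3.
4. Keep last observation carried forward in the MITT principal analysis, and add a sensitivity analysis that scores the measured value. State whether a woman whose only collection is invalid stays in the MITT.
5. Reconcile the sentence that includes all reported values with the list of invalidity grounds.

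The cost is SAP wording and one further analysis, with no new data collection. The ITT success rate may be marginally lower.

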9.2 Primary Efficacy Variables

The primary outcome measure will be the proportion of subjects with successful treatment of heavy menstrual bleeding based on the decrease in MBL from baseline to end of treatment after initial LNG20 IUS insertion. For the MITT and PP analysis populations, end of treatment will be defined as the last post baseline MBL value (either Treatment Cycle 3 or Treatment Cycle 6) recorded for the subject.

For the ITT-based analysis population, subjects who lack both a Treatment Cycle 3 and Treatment Cycle 6 MBL result will have the baseline MBL serve as the end of treatment recorded outcome.

A subject with successful treatment will be defined as:

- the end of treatment MBL <80 mL, and
- a decrease to a value of no greater than 50% of the baseline MBL.

9.3 Key Secondary Efficacy Variables

All key secondary outcomes will be summarized by descriptive statistics using the MITT Population except that the bleeding and/or spotting analyses will be summarized using both Safety and MITT Populations. The subgroup analysis of absolute change in the median MBL from baseline to End-of-study will assess differences for age, race/ethnicity, and BMI subgroups, no formal statistical testing will be performed.

Menstrual Blood Loss:

- Absolute change in baseline MBL to mid-treatment MBL (Cycle 3)
- Percent change from baseline MBL to mid-treatment MBL (Cycle 3)
- Absolute change from baseline to end of treatment (Cycle 6), including subgroup analysis for age, race/ethnicity, and BMI

- Percent change from baseline MBL to end of treatment MBL (Cycle 6)

Vaginal Bleeding Flow:

- Vaginal bleeding flow (none, spotting, and light, normal, or heavy flow [bleeding]) will be summarized based on the daily diary by incidence and duration of bleeding at each Cycle. Vaginal bleeding is recorded on the daily diary during the Screening Phase and baseline will be considered the cycle with the worst flow severity during the screening cycles.
 - Based on World Health Organization (WHO) terminology, bleeding and spotting are defined as:
 - Bleeding: any bloody vaginal discharge for which protection, such as pads is used
 - Spotting: any bloody vaginal discharge for which protection is not used; if spotting and bleeding occur on the same day, it is recorded as a bleeding day
 - Incidence of bleeding by 28-day cycle intervals post-insertion (none vs. spotting vs. bleeding; none vs. ≥ 1 day; 1-3, 4-7, >7, and >20 days; no bleeding vs. any bleeding) will be summarized
- Vaginal Bleeding Episodes
 - Based on the individual subject's daily diary of bleeding
 - A bleeding day is when sanitary protection is used
 - A bleeding episode is defined as light, normal or heavy bleeding during a minimum of one day as defined by a subject's subjective assessment
 - A bleeding-free day is defined as a day with either no bleeding or only spotting
 - A single bleeding episode will consist of all bleeding days separated by no more than one bleeding-free day. Separate bleeding episodes will consist of bleeding days separated by more than one bleeding-free day. An episode will be considered stopped with two consecutive bleeding-free days.

- Bleeding will be summarized by the number and percentage of days with a particular pattern during each 28-Day interval after enrollment through Cycle 6 or IUS Discontinuation.
- Absolute changes and percentage changes from baseline to Cycle 3, from baseline to Cycle 6, and from Cycle 3 to Cycle 6 of the Treatment Phase will be calculated for the following bleeding pattern indices:
 - Total number of days of bleeding
 - Total number of days that include spotting or bleeding
 - Total number of days that include spotting only
 - Total number of bleeding episodes
 - The baseline numbers are the average of the Screening cycles evaluated

The subjective assessment of the impact of the LNG20 IUS on menstrual bleeding severity, dysmenorrhea, pelvic pain and daily activities will be assessed using a 10 cm Visual Analog Scale (VAS) questionnaire with appropriate questions. The VAS questionnaires will be completed and collected at baseline (Visit 5), and after 3 cycles (Visit 7) and 6 cycles (Visit 8):

- VAS scores for each question will be summarized for baseline, Cycle 3, and Cycle 6.
- VAS changes from baseline to mid-treatment (Cycle 3), from mid-treatment (Cycle 3) to end of treatment (Cycle 6) and from baseline to end of treatment (Cycle 6) will be summarized for each question.

10. METHODS OF EFFICACY ANALYSIS

10.1 Primary Efficacy Outcome

The primary efficacy analysis of the proportion of subjects with successful treatment of HMB from baseline to end of treatment (based on the last post baseline MBL value up to Treatment Cycle 6) will be presented with 95% confidence interval based on normal approximation of binomial distribution.

Subjects who are lost-to-follow-up (LT FU) or withdrew consent prior to Treatment Cycle 6 evaluation are considered a subset with truly missing information. In particular, within

the context of the Covid-19 pandemic, it could be reasonably argued that they may simply have been unable or unwilling to appear for an investigational site visit. Therefore, in order to evaluate the appropriateness of procedures for handling missing data, the following approaches to data analysis will be used (as described in SAP [Sections 5.3.3 and 6](#)):

1. MITT population with LOCF: results from this approach will be considered the principal analysis finding for this study.
2. ITT population with LOCF.
3. ITT population excluding subjects LTFU or withdrew consent without study IUS removal with LOCF.

Additional assessments using the supportive MITT and PP populations will be conducted as mentioned in SAP [Section 6](#).

